5.3.2 Eliciting Adverse Event Information

The investigator is to report all directly observed AEs and all AEs spontaneously reported by the patient. In addition, each study patient will be questioned about AEs.

5.3.3 Assessment of Adverse Event Severity

The adverse event severity grading scale for the NCI CTCAE (v 4.0) will be used for assessing adverse event severity. All appropriate treatment areas should have access to a copy of the CTCAE version 4.0. A copy of the CTCAE version 4.0 can be downloaded from the CTEP web site http://ctep.cancer.gov/protocolDevelopment/electronic_applications/ctc.htm. The grading system below will be used for assessing severity for adverse events that are not specifically listed in the NCI CTCAE.

Grade	Severity
1	Mild; asymptomatic or mild symptoms; clinical or diagnostic observations only; or intervention not indicated
2	Moderate; minimal, local, or non-invasive intervention indicated; or limiting age-appropriate instrumental activities of daily living ^a
3	Severe or medically significant, but not immediately life-threatening; hospitalization or prolongation of hospitalization indicated; disabling; or limiting self-care activities of daily living ^{b,c}
4	Life-threatening consequences or urgent intervention indicated ^d
5	Death related to adverse event ^d

Legends:

^a Instrumental activities of daily living refer to preparing meals, shopping for groceries or clothes, using the telephone, managing money, etc.

^b Examples of self-care activities of daily living include bathing, dressing and undressing, feeding one's self, using the toilet, and taking medications, as performed by patients who are not bedridden.

^c If an event is assessed as a "significant medical event," it must be reported as a serious adverse event,

^d Grade 4 (only if immediately life threatening) and 5 events must be reported as serious adverse events

5.3.4 Assessment of Causality of Adverse Events

Investigators should use their knowledge of the patient, the circumstances surrounding the adverse event, and an evaluation of any potential alternative causes to determine whether or not an adverse event is considered to be related to the IP or Non-IP, indicating "yes" or "no" accordingly. The following guidance should be taken into consideration:

- Temporal relationship of event onset to the initiation of study drug
- Course of the event, considering especially the effects of dose reduction, discontinuation of study drug, or reintroduction of study drug (where applicable)
- Known association of the event with the study drug or with similar treatments
- Known association of the event with the disease under study
- Presence of risk factors in the patient or use of concomitant medications known to increase the occurrence of the event
- Presence of non-treatment-related factors that are known to be associated with the occurrence of the event

Adverse Event Attribution Categories:

Definitely	Direct association with study agent; clearly related
Probably	More likely explained by study agent
Possibly	Study agent and other cause explained equally well; maybe related
Probably Not	More likely explained by other cause; doubtfully related to the intervention
Unrelated	Clearly explained by other cause; clearly NOT related to the intervention

5.3.5 Procedures for Recording Adverse Events

5.3.5.1 Abnormal Laboratory Values

The criteria for determining whether an abnormal objective test finding should be reported as an AE are as follows:

- Test result is associated with accompanying symptoms; and/or
- Test result requires additional diagnostic testing or medical/surgical intervention; and/or

- Test result leads to a change in study dosing, or discontinuation from the study, significant additional concomitant drug treatment, or other therapy; and/or
- Test result is considered to be an AE by the investigator or Sponsor
- Test causes delay of definitive surgery.

Merely repeating an abnormal test, in the absence of any of the above conditions, does not constitute an AE. Any abnormal test result that is determined to be an error does not require reporting as an AE.

5.4.2 Serious Adverse Events Reporting Requirements

5.4.2.1 Reporting of Serious Adverse Events

When learning about and SEA (SAEs definition **section 5.2.2**), the Sponsor PI or their designee will notify:

1. The IRB and DSMC by a written safety report within one (1) business day of learning of the SAE;
2. Pfizer by facsimile within seven (7) calendar days of the first awareness of the event (immediately if the event is fatal or life-threatening), if:
 - Study subjects who are assigned to receive the Pfizer Product Palbociclib; or
 - Individuals otherwise exposed to the Pfizer Product as described below.

The Sponsor PI will provide additional details about the SAE to the IRB and DSMC, as well as Pfizer as it becomes available. Sponsor Principal Investigator should report SAEs as soon as they are determined to

meet the definition, even if complete information is not yet available. Within the following 1-2 business days of awareness, the participating investigator must provide follow-up information on the serious adverse event if a full description of events was not included with the initial reporting of the event to Sponsor PI. Follow-up information should describe whether the event has resolved or continues, if and how the event was treated, and whether the participant will continue or discontinue study participation. Sub-investigators should submit this information to the Sponsor PI at [REDACTED].

Additional information that should be reported as SAEs include data related to overdose, abuse, off-label use, misuse, inadvertent/erroneous administration, medication error or occupational exposure, with or without association with an AE/SAE unless otherwise specified in the protocol.

All non-serious adverse events will be reported to the Sponsor on the adverse events CRFs.

As used in this Agreement, the term SAE will be understood to include exposure during pregnancy, exposure during lactation, and occupational exposure (refer to **section 5.4.2.2**).

5.4.2.2 Exposure during Pregnancy, Exposure during Lactation, Occupational Exposure

Even though there may not be an associated SAE, exposure to the Pfizer Product Palbociclib during pregnancy, during lactation, and occupational exposure are reportable. Abortions and congenital anomalies should also be reported.

5.4.2.3 Hy's Law Cases

Cases of potential drug-induced liver injury as assessed by laboratory test values ("Hy's Law Cases") are also reportable to Pfizer. If a Study subject develops abnormal values in aspartate transaminase (AST) or alanine transaminase or both, concurrent with abnormal elevations in total bilirubin and no other known cause of liver injury, that event would be classified as a Hy's Law Case. As used in this Agreement, the term SAE will be understood to also include Hy's Law Cases.

5.4.2.4 SAE Reporting Period

The SAEs that are subject to this reporting provision are those that occur from after the first dose of Palbociclib through 28 calendar days after the last administration of the Pfizer Product. In addition, if Principal Investigator becomes aware of an SAE occurring any time after the administration of the last dose of the Palbociclib, Sponsor PI should report that SAE to Pfizer if a causal relationship between the Pfizer Product and the SAE is suspected.

5.4.2.5 Follow-Up Information

Principal Investigator will assist Pfizer in investigating any SAE and will provide any follow-up information reasonably requested by Pfizer.

5.4.2.6 Regulatory Reporting

Reporting an SAE to Pfizer does not relieve Principal Investigator of responsibility for reporting it to appropriate regulatory authorities, if such reporting is required.

5.4.2.7 Pfizer-Provided Training

Pfizer will make available training material that provides information about the SAE reporting requirements for IIR studies like this. Principal Investigator will review this material and share it with any Study staff engaged in the reporting of SAEs.

5.4.3 Non-Serious Adverse Event Reporting Requirements

All AEs will be reported on the AE page(s) of the CRF.

The Sponsor PI will forward periodically listings of non-serious AEs originating from the study to Pfizer.

5.4.3.1 MedWatch 3500A Reporting Guidelines

In addition to completing appropriate patient demographic and suspect medication information, the report should include the following information within the Event Description of the MedWatch 3500A form:

- Protocol description (and number, if assigned)
- Description of event, severity, treatment, and outcome if known
- Supportive laboratory results and diagnostics
- Investigator's assessment of the relationship of the adverse event to each investigational product and suspect medication

MedWatch 3500A (Mandatory Reporting) form is available at

<http://www.fda.gov/medwatch/getforms.html>

5.4.4 Sponsor PI Reporting Requirements to Regulatory Authorities

Adverse event reporting, including suspected unexpected serious adverse reactions, will be carried out in accordance with applicable local regulations.

5.4.4.1 Seven Calendar Day Telephone or Fax Report:

The Sponsor PI is required to notify the FDA of any fatal or life-threatening adverse event that is unexpected and assessed by the Investigator to be possibly related to the use of palbociclib. An unexpected adverse event is one that is not already described in the palbociclib Investigator Brochure. Such reports are to be telephoned or faxed to the FDA and Pfizer within 7 calendar days of first learning of the event.

5.4.4.2 Fifteen Calendar Day Written Report

The Sponsor PI is also required to notify the FDA and all participating investigators, in a written IND Safety Report, of any serious, unexpected AE that is considered reasonably or possibly related to the use

of Palbociclib. An unexpected adverse event is one that is not already described in the Palbociclib investigator brochure.

Written IND Safety reports should include an Analysis of Similar Events in accordance with regulation 21 CFR § 312.32. All safety reports previously filed by the Sponsor PI with the IND concerning similar events should be analyzed and the significance of the new report in light of the previous, similar reports commented on.

Written IND safety reports with Analysis of Similar Events are to be submitted to the FDA, Pfizer and all participating investigators within 15 calendar days of first learning of the event. The FDA prefers these reports on a MedWatch 3500 form, but alternative formats are acceptable (e.g., summary letter).

FDA fax number for IND Safety Reports:

Fax: [name]

All written IND Safety Reports submitted to the FDA by the Investigator must also be faxed to Pfizer U.S. Clinical Trial Department at [REDACTED] (Cover sheet at Appendix K)

And to the Site IRB:

MedStar Georgetown University Hospital - Institutional Review Board
[name]
[name]
[name]
[REDACTED]
[REDACTED]
[REDACTED]

5.4.5 Reporting Forms:

Principal Investigator will report SAEs using a CIOMS I form (<http://www.cioms.ch/index.php/cioms-form>) or MedWatch 3500A (available at <http://www.fda.gov/medwatch/getforms.html>). The Reportable Event Fax Cover Sheet (Appendix K) provided by Pfizer must also be included with each SAE submitted.

The SAE Reporting Checklist is below:

- Use DD/MMM/YYYY format.
- Record all pertinent information on the SAE Report Form. **Do NOT** attach source documents (e.g., test results).
- Do NOT delay completing and submitting the SAE Report Form in order to obtain further information that could be submitted as a follow-up report.
- If a definitive assessment of causality is not possible at the time of the report, provide a preliminary assessment on the SAE page, and identify it as such in the **Event Narrative**.
- If the SAE is not deemed causally related to a study drug by the investigator, indicate in the **Event Narrative** the most likely cause (disease under study, other illness, etc.).
- If additional space is needed for any field, use additional copies of the same page.

- Use a new SAE Report Form when providing follow-up information or responding to queries. Do NOT cross out or add to the previous form.
- Obtain safety reporting contact information for your study from your Pfizer contact.
- Confirm not only that a faxed SAE Report Form was transmitted successfully, but also that it was transmitted to the correct fax number.

5.4.6 IND Annual Reports

All IND annual reports submitted to the FDA by the Sponsor-Investigator should be copied to Pfizer.

5.4.7 Data Safety Monitoring Committee

As this study is an investigator initiated study utilizing FDA approved agent it is considered a moderate risk study which requires real-time monitoring by the Sponsor PI and study team and semiannual reviews by the LCCC Data and Safety Monitoring Committee (DSMC).

The Principal Investigator and the Co-Investigators will review the data including safety monitoring at weekly disease group meetings and on monthly network disease group teleconferences. The investigators shall meet regularly to review toxicities and follow up on results of patients enrolled on the study.

Progress on the trial and the toxicities experienced will be reviewed by the Lombardi Comprehensive Cancer Center Data and Safety Monitoring Committee every 6 months from the time the first patient is enrolled on the study. Results of the DSMC meetings will be forwarded to the IRB. E-mail notification from the Sponsor PI will be sent to the DSMC Chair any time there is a major event or issue with the trial affecting patient safety or conduct of the trial. The DSMC Chair has the discretion to have the study reviewed by the DSMC sooner more frequently than every 6 months based on information received.

All Severe Adverse Events (SAEs) are required to be reported to the IRB. In addition, all SAEs will be submitted to the DSMC at time of submission to IRB and to Pfizer. Based on SAEs, the IRB retains the authority to hold accrual for the study pending more detailed reporting and/or modifications to further reduce risk and maximize the safety of participating patients. DSMC recommendations should be based not only on results for the trial being monitored as well as on data available to the DSMC from other studies. It is the responsibility of the Sponsor PI to ensure that the DSMC is kept apprised of non-confidential results from related studies that become available. It is the responsibility of the DSMC to determine the extent to which this information is relevant to its decisions related to the specific trial being monitored.

A written copy of the DSMC recommendations will be given to the trial Sponsor PI and the IRB. If the DSMC recommends a study change for patient safety or efficacy reasons the investigator must act to implement the change as expeditiously as possible. In the unlikely event that the Sponsor PI does not concur with the DSMC, then the Lombardi Cancer Center Associate Director of Clinical Research must be informed of the reason for the disagreement. The Sponsor PI, DSMC Chair, and the Lombardi Cancer Center ADCR will be responsible for reaching a mutually acceptable decision about the study. Confidentiality must be preserved during these discussions. However, in some cases, relevant data may be shared with other selected trial investigators and staff to seek advice to assist in reaching a mutually acceptable decision.

If a recommendation is made to change the trial for reasons other than patient safety or efficacy the DSMC will provide an adequate rationale for its decision.

6. STATISTICAL CONSIDERATIONS AND ANALYSIS PLAN

6.1 Determination of Sample Size

There will be two participating centers in this study: MGUH and MWHC. This is a prospective pilot study designed to assess the feasibility and potential translational changes of preoperative treatment with palbociclib of patients with Rb positive DCIS of the breast. The primary endpoints are feasibility and pathologic changes (histology, IHC and molecular analysis) comparing paired samples from before and after short course of systemic treatment (diagnostic core vs definitive surgery, in each patient). The secondary endpoint is descriptive toxicity.

The estimated sample size of 12 patients per study Group is decided based on typical sample size requirement for a pilot study⁵⁶ because parameters for expected pathologic changes caused by palbociclib in this disease are not available. *The total number of patients in this study will be 24.* The statistical analysis will be mostly descriptive due to the nature of the study and the small sample size. It will be performed after study completion. Baseline and follow-up data will be summarized using basic descriptive statistics such as means and standard deviations for the continuous variables and frequencies and percentages for categorical variables. For continuous outcome, the median and range will be reported. For binomial outcome, the proportion will be estimated along with its confidence interval estimated using exact method. Changes in the tumor histologic or molecular parameters from baseline to end of treatment will be tested using paired t-tests for continuous variables and McNemar's test for paired proportions. Repeated measures data will be analyzed using linear growth curve models that will allow us to identify and estimate individual-level growth tracks for the patients. Survival models (time to event) will be used as sample size permits to evaluate disease progression among all patients.

LCCC Biostat Unit will be responsible for designing the study and conducting data analysis which will be directed by [name].

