Decreased appetite	16	1	0	8	1	0
Nervous system disorders						
Headache	26	1	0	20	0	0
Dysgeusia	7	0	0	3	0	0
Respiratory, thoracic and mediastinal disorders						
Epistaxis	7	0	0	2	0	0
Gastrointestinal disorders						
Nausea	34	0	0	28	1	0

In a phase I study ⁴², palbociclib related neutropenia and thrombocytopenia occurred around day 21, the end of 21-day period of continuous PO daily dose in a 28-day cycle. In cycle 1, rebound of both ANC and platelet levels were observed during the off-drug period that continued up to day 8 of the following dosing cycle.

[figure not shown]

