2.3 Outcome Measures

Feasibility: the approach will be considered feasible if more than 50% of the enrolled patients are treated and followed within protocol rules, if collected samples are suitable for studies, and if pathologic changes are detectable when comparing diagnostic and surgical specimens, or treated and untreated specimens. In Group A, patients will be treated with palbociclib alone, providing the opportunity to address if proposing this kind of treatment for these patients is feasible. Obtaining human data and feasibility data would be key for designing efficacy/definitive studies of palbociclib in DCIS.

Pathology: we will perform descriptive analysis of microscopic and molecular changes upon exposure to palbociclib. Biological markers will be tested by immune histochemistry (IHC). Source for comparison will be pretreatment versus post-treatment paired samples. This study will represent an opportunity to describe potential pathological changes triggered by palbociclib as a single agent in DCIS.

Toxicity: will be evaluated by CTCAE. There is no plan to compare Groups A and B regarding efficacy or toxicity. Toxicity will be descriptive for each treatment group, independently.

Correlative science: Will be performed at Lombardi Comprehensive Cancer Center. Preliminary data for this proposal was obtained using a well-established model of DCIS progression with the human MCF-DCIS cell line^{45,47}. Proposed translational components are currently routinely done at LCCC. There is no plan to compare Groups A and B regarding translational changes. Paired samples (pre- and post-systemic therapy) will be compared within the respective Group. **DCIS Sample #1** is the core biopsy

done for diagnosis, **DCIS Sample #2** is collected at definitive surgery; both collected from the same patient (paired).

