4.5.2.7 Mandatory Blood Samples for Biomarker Analysis

During screening phase blood samples will also be collected for storage at the Lombardi Biorepository. These are research samples.

Group A: In Group A there will be 3 time points for research blood collection.

1. The first research blood samples will be collected after consenting and prior to palbociclib treatment.
2. The second research blood sample will be collected after end of palbociclib and prior to surgery, typically on the date of surgery.
3. The third research blood sample will be collected after surgery (End of treatment visit).

Group B: In Group B there will be 2 time points for research blood collection.

1. The pre-operative research blood sample can be collected any time after consenting and prior to surgery in Group B.
2. The second research blood sample will be collected after surgery (End of treatment visit).

Appendix M contains the **Research Blood Sample Form**, to be filled on the day of sample collection and handling until its storage. Samples from this project will be stored at the [name] Lab.

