4.5.4 Pre-Surgery phase

For patients enrolled to **Group A**, on Day 13 +/-1 there will be a pre-operative clinic visit, when tolerance to therapy will be assessed, including physical examination/vital signs, ECOG performance status assessment, adverse events, serious adverse events, IP accountability, concomitant medications, measurements of treatment adherence. Laboratory tests will include CBC, CMP and an additional blood sample for research (please refer to item **4.5.2.7 Mandatory Blood Samples for Biomarker Analysis**). After this visit, patients will proceed to scheduled definitive surgery for DCIS. Treatment phase ends on the day of surgery (Day 15 +/-1).

For patients enrolled to **Group B** the pre-surgery experimental phase will only involve Laboratory tests including CBC, CMP and an additional blood sample for research (please refer to item **4.5.2.7 Mandatory Blood Samples for Biomarker Analysis**).

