Appendix A: Study procedures

	Screening Phase		Treatment Phase		Pre-surgery	Surgery	Follow up Phase	
Procedure	Screening	Pre-treatment	Treatment start	Last day of treatment	Pre-surgery	Day of Surgery	End of Treatment visit	Long term follow up
Day	(-28 to -1)	(-28 to 0)	1	12	13 +/-1	15 +/-1	32 (+/- 8 days)	1yr and 5yr
Signed Informed Consent Form(s)	x							
Review of Eligibility Criteria	x	x						
Clinical Visit	x ⁹	x ⁷			x ⁷		x	
Review of breast US, Mammograms and breast MRI if available	x							
Disease status	x	x ⁴			x ⁴		x	x ⁶
CTCAE v. 4.03 review of baseline toxicities		x			x ⁴		x	
Archival tumor tissue specimen or 15 unstained slides	x							
Rb testing archival tissue	x ¹							
Tissue for research at definitive surgery						x ⁵		
CBC/diff/platelets	x ⁸	x ⁴			x ⁴		x	
CMP	x ⁸	x ⁴			x ⁴		x	
Coags (aPTT, INR)	x ⁸							
Serum or urine pregnancy test	x							
Blood sample for research - cells		x ²			x ^{2,4}		x ²	

	Screening Phase		Treatment Phase		Pre-surgery	Surgery	Follow up Phase	
Procedure	Screening	Pre-treatment	Treatment start	Last day of treatment	Pre-surgery	Day of Surgery	End of Treatment visit	Long term follow up
Day	(-28 to -1)	(-28 to 0)	1	12	13 +/-1	15 +/-1	32 (+/- 8 days)	1yr and 5yr
Schedule definitive surgery date		x						
Group A: Start palbociclib			x ³					
Group B: no treatment								
Lumpectomy or mastectomy						x		
Pathologic exam of specimen						x		
EMR review							x	1yr and 5yr
Telephone contact							x	1yr and 5yr

1 Rb testing for all participants at screening. Rb negative configures screen failure.

2 Research blood sample for liquid biopsy and tissue banking (serum/plasma and PBMCs). In Group B, pre-operative sample can be drawn any time after consenting and prior to surgery. For details on these samples please refer to item **4.5.2.7 Mandatory Blood Samples for Biomarker Analysis**

3 Palbociclib 100mg PO daily for 12 days; provided by Pfizer and to be dispensed by MGUH/WHC research pharmacy.

4 Group A only.

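### If the linear growth curve in Section 6.1 means a straight line in time, it blends on-drug and off-drug change in Group A serial blood; visit contrasts would not

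*Combined protocol and SAP*

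**What the plan says.** Section 6.1 has one sentence on repeated measures: "Repeated measures data will be analyzed using linear growth curve models that will allow us to identify and estimate individual-level growth tracks". It does not say what function of time is meant. Tumor tissue is dealt with separately in the sentence before: "Changes in the tumor histologic or molecular parameters from baseline to end of treatment will be tested using paired t-tests for continuous variables", with McNemar's test for paired proportions.

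Section 4.5.2.7 sets out the research blood: "In Group A there will be 3 time points for research blood collection". The first sample is taken before palbociclib. For the second, "The second research blood sample will be collected after end of palbociclib and prior to surgery, typically on the date of surgery". The third is taken after surgery, at the end-of-treatment visit. Section 4.5.4 also places a research sample at the pre-surgery visit: "on Day 13 +/-1 there will be a pre-operative clinic visit". Appendix A schedules CBC and CMP in Group A at screening, pre-treatment, pre-surgery and the end-of-treatment visit, which is up to four draws.

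The last dose is on Day 12 (Section 3.1.1), and the last visit is on Day 32 with a margin of 8 days (Section 4.5.6 and Appendix A). On the shape of the response off drug, Section 1.2.5 reports from a phase I study that "rebound of both ANC and platelet levels were observed during the off-drug period". Nothing comparable is given for any research-blood marker.

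**The concern.** Group A blood is drawn before exposure, just after it, and again well after it has ended. A marker that responds to the drug need not move in one direction across those three occasions. A straight line has one slope for the whole span, so the off-drug segment pulls on the estimate of what happened on drug. For the two counts on which the protocol does describe off-drug behavior, the segments run in opposite directions.

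The informative quantity in this series is the change from the last pre-dose value to the post-drug value. If the fitted line is read as describing that change, it can shrink it, and with full rebound it can nearly cancel it. The data concerned are secondary: correlative blood and laboratory series in a small pilot meant to inform a later study.

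**Working it through.** The plan gives no figure for this analysis, so there is none to reproduce. The check asks how much of a known on-drug change a least-squares line would imply.

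**Inputs from the documents (Group A)**
- First research sample, t1: Day -28 to 0 (Appendix A, pre-treatment column).
- Post-drug sample, t2: Day 12 to 16. Section 4.5.4 gives Day 13 +/-1. Section 4.5.2.7 allows the day of surgery, which is Day 15 +/-1.
- Last sample, t3: Day 24 to 40 (32 +/-8). This is 24 - 12 = 12 to 40 - 12 = 28 days after the last dose.

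**Assumption**
- r is the share of the on-drug change that is lost again by t3. The documents do not give it. The range runs from r = 0 (plateau) to r = 1 (full rebound).

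**Formula.** Set the true profile to 0 at t1, -1 at t2 and -(1 - r) at t3. With m the mean of the three days, slope = sum[(t - m) y] / sum[(t - m)²]. The share of the true change that the line implies is -slope × (t2 - t1). With complete data at common visit times, this slope equals the fixed slope of a random intercept-and-slope growth curve.

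**Worked case, Days 0, 13, 32.** m = 15 and the deviations are -15, -2 and 17. The denominator is 225 + 4 + 289 = 518. The numerator is 2 - 17(1 - r).
- r = 0: slope = -15/518, share = 13 × 15/518 = 37.6%
- r = 0.5: slope = -6.5/518, share = 13 × 6.5/518 = 16.3%
- r = 1: slope = +2/518, share = -13 × 2/518 = -5.0%

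**Other schedules for research blood**

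| Days (t1, t2, t3) | Plateau | Half rebound | Full rebound |
|---|---|---|---|
| 0, 15, 32 | 45.8% | 21.9% | -2.0% |
| -28, 13, 32 | 73.4% | 44.7% | 16.0% |
| -28, 15, 32 | 77.2% | 48.3% | 19.5% |
| 0, 12, 40 (lowest in the windows) | 24.7% | 8.5% | -7.6% |
| -28, 16, 24 (highest in the windows) | 89.8% | 61.7% | 33.7% |

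The last two rows are the extremes over every whole-day combination in the windows. The share is linear in r, so it stays below 100% for any r from 0 to 1.

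**CBC and CMP at four draws** (screening, pre-treatment, Day 12 to 14, Day 24 to 40, with both pre-dose values at 0): 20 to 87% with a plateau, 12 to 61% with half rebound, -1 to 34% with full rebound.

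**When the direction reverses.** The line is exact only if the third point lies on the line through the first two. At Days -28, 15, 32 that needs a third value of -60/43 = -1.40, a further off-drug fall of 0.40 times the on-drug change. Beyond that the line overstates: a further fall of 0.5 gives 106%, and a further fall of 1 gives 135%.

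**Visit contrast.** The post-drug minus pre-dose difference recovers 100% whatever r is. With 12 patients its 95% interval has half-width 2.201/√12 = 0.64 standard deviations of the paired change.

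**The case against.** The strongest reply is that the plan never says a slope will be reported as the on-drug change. It says the models serve to describe individual tracks, and a linear model could include visit as a factor or a bend at the end of dosing. That stands. If visit is already a factor, the problem disappears, so the point is conditional on the straight-line reading.

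It is also uncertain that the sentence covers blood. A reader might infer that blood is the only series with enough occasions, but vital signs are also taken at screening, pre-surgery and the last visit (Sections 4.5.2.4, 4.5.4 and 4.5.6). Section 2.3 says toxicity will be graded by CTCAE and described by group, so applying the model to CBC and CMP is a further inference.

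A reader might also infer that the line must understate drug effects. The documents do not support that, because they give no off-drug shape for research-blood markers and continued decline can reverse the direction. Nor do they support a general claim of lost power or poor interval coverage, since they give no standard deviation. For illustration only, a one-unit fall with 12 patients at two-sided 0.05 gives the paired test about 88% power if the unit is the SD of the change, and about 61% if it is the residual SD. No such figure is relied on here.

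Much of the plan already points the right way. Descriptive summaries of baseline and follow-up data are planned, and for correlative science Section 2.3 says "Paired samples (pre- and post-systemic therapy) will be compared within the respective Group", although its next sentence defines tissue samples only. This lowers the stakes but does not change the model named in Section 6.1.

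**Conclusion.** The point holds in a conditional form, as a minor improvement. It needs three things: the growth curve is a straight line in time, it is applied to Group A serial blood, and the marker plateaus or rebounds after the last dose. Under those conditions the line understates the baseline-to-post-drug change in every allowed window, by the shares shown above. The size depends on the assumed rebound and on how early the baseline sample is drawn.

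It would be wrong to read this as a threat to the primary comparison. Tissue has two samples per patient and its own paired tests. Appendix A describes research blood as being for liquid biopsy and banking, and no blood marker, hypothesis or decision rule depends on the growth curve. Group B has two research samples under Section 4.5.2.7, so a per-patient line there simply reproduces the paired difference.

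The documents also differ on the timing of the last visit and on the Group B blood time points. Those are separate matters to reconcile, and this conclusion does not depend on them.

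**What to change.** For Group A series that span drug exposure and washout, replace the straight-line trend in Section 6.1 with visit contrasts. Suggested wording:

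*Serial Group A measurements that span palbociclib exposure and washout will be analyzed by visit, using a mixed model with visit as a categorical factor and a patient random intercept, or paired differences. Post-drug minus last pre-dose value and last visit minus baseline will each be reported with a 95% confidence interval. Individual profiles will be plotted.*

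The plots keep the aim of describing individual tracks. The cost is one sentence of analysis text, with the same samples and simpler programming. The downside is that no single per-patient slope is estimated.
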